Appendix A – Abdominal Surgeries Considered for Study Inclusion

- Pancreatic resection
- Splenectomy
- Any gastrectomy (partial or total)
- Hiatal hernia repair
- Any gastric fundoplication
- Esophagectomy with planned intra-abdominal component
- Any hepatic resection
- Common bile duct exploration
- Resection of retroperitoneal sarcoma
- Any nephrectomy (partial or total)
- Hyperthermic intraperitoneal chemotherapy (HIPEC)
- Any colonic resection
- Colostomy or ileostomy takedown
- Repair of enterocutaneous fistula
- Open abdominal aortic aneurysm (AAA) repair
- Adrenalectomy

Additional operations will be considered for inclusion if the study team and primary surgical team both agree that the procedure is a major abdominal surgery, that the expected duration of the surgery will be \geq 120 minutes, and the expected post-operative hospital length of stay will be \geq 2 days.

Appendix B – Medications that would preclude subject enrollment

Sulfonylurea anti-diabetic agents

- Acetohexamide
- Carbutamide
- Chlorpropamide
- Glibenclamide (also known as glyburide)
- Glibornuride
- Gliclazide
- Glyclopyramide
- Glimepiride
- Glipizide
- Gliquidone
- Glisoxepide
- Tolazamide
- Tolbutamide

Nitrates

- Nitroglycerine (glyceryl trinitrate)
- Isosorbidemononitrate and dinitrate
- Itramin
- Pentaerithrityltetranitrate
- Propatylnitrate
- Tenitramine
- Trolnitrate
- Nicorandil

# Appendix C: Statistical Analysis Plan

# I. Introduction

This plan provides a detailed description of the study endpoints, methods of data analyses and other relevant issues pertaining to a prospective randomized controlled trial of remote ischemic conditioning in patients undergoing major abdominal surgery at a single institution.

# II. Study endpoints

II.1 Primary endpoint: 30 days postoperative complications

**II.1.a** The total complications burden up to 30 days after surgery will be evaluated with the use of comprehensive complications index (CCI, [range 0-100]).

## II.2 Secondary enpoints

a) Length of hospital stay: number of days from surgery to discharge from hospital

b) 30-day mortality: (% subjects dying within 30 days)

c) Cytokine response: plasma levels (pg/mL) of TNF-a, IL - 1 $\beta$ , 6, 8 and 10

d) Acute phase response: Plasma levels of C-reactive protein (CRP),  $\alpha$ -1 acid glycoprotein, fibrinogen and haptoglobin (mg/dL)

e) Complement activation: Plasma levels of C2, C4b, C5a and C5b-9 (mg/dL)

f) Leukocyte gene expression: Global gene expression changes in peripheral blood leukocytes

#### II.3 Feasibility/Acceptability endpoints

Feasibility: proportions of subjects completing all 3 assigned research interventions, not withdrawing participation and completing follow up after enrollment.

Acceptability: proportions of subjects not declining any of the 3 planned research interventions

## II.4 Safety endpoints

- a) Adverse events (AE)
- b) Serious adverse events (SAE)
- c) Adverse reactions (AR)
- d) Suspected serious adverse reactions (SSAR)
- e) Suspected unexpected serious adverse reactions (SUSAR)

The definitions of the safety endpoints are as per ICH Harmonized Tripartite Guideline for clinical safety data management E2A version 4.

## III. Analyses populations

**III.1** The primary analyses for efficacy will be conducted in an "**intent to treat (ITT) population** " that would include all randomized subjects.

**III.2** Additional secondary analyses for efficacy will be conducted in "**per protocol (PP) population**" that would include only subjects that completed all three interventions and follow up.

**III.3** The **Safety population** for analyses of safety endpoints will include all subjects that received at least one of the assigned interventions.

# IV. Descriptive analyses

Demographic and clinical baseline characteristics will be summarized for each of the study groups. Data for continuous variables will be reported with point estimates (mean or median) and dispersion measures (standard deviation, 25th and 75th percentiles, 95% confidence intervals). Data for discrete variables will be reported as counts and proportions in each group. Counts of subjects with data missing for each variable will be reported.

No formal comparisons of the differences between the two groups are planned at present.

# V. Analyses of study endpoints

#### V.1 Primary endpoint

Comprehensive complications index score will be compared between the two groups to examine the effect of RIC on postoperative complication. Data transformation may be utilized to achieve normality. One of two independent sample tests, a t test or Mann-Whitney test depending on the normality of distribution, will be used. Using multivariable regression exploratory analyses will be conducted to examine potential interactions of individual variables of age, sex and duration of surgery with RIC on CCI. P values of 0.05 will be considered significant.

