Major abdominal surgery is associated with a high risk of post-operative complications. Up to 16.4% of all general surgery patients may have at least one complication. This proportion increases with the complexity of the surgery.² More severe complications are associated with death and longer hospital stay.² One of the common pathways contributory to an increase in complications is excessive systemic inflammation in response to the stress of surgery. In one study, plasma levels of C-reactive protein (CRP), an acute-phase reactant and marker of inflammation, as well as interleukin (IL) 6 (a known pro-inflammatory cytokine), were increased in trauma patients with multi-organ dysfunction syndrome (MODS) compared to those without organ dysfunction.³ By contrast, levels of IL-10, an anti-inflammatory cytokine, were decreased in patients with MODS.³ Another study confirmed these findings in major abdominal surgery; plasma levels of pro-inflammatory cytokines IL-6 and IL-8 were increased, although levels of the

anti-inflammatory cytokine IL-10 were also increased.⁴ This study and another by the same group also showed activation of the complement cascade with surgery, both via the classical and alternate pathways.^{4,5} Thus, major abdominal surgery induces significant changes in the innate immune system, changes that may be excessive and may contribute to complications after surgery in some patients.

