- 8. Prior major surgery during current hospitalization (for instance, a patient undergoing relaparotomy for a complication from a previous procedure)
- Patient taking sulfonylureas or nitrates prior to or during admission (listed in Appendix B)
 - a. These subjects are excluded because sulfonylureas are shown to abrogate the RIC effect whereas nitrates are shown to mimic the RIC effect in animal models.
- 10. Non-elective surgeries (urgent or emergent surgeries)
- 11. General surgical procedures with no planned intra-abdominal component

VII. RESEARCH METHODS:

VII.1 Recruitment and enrollment: Eligible candidates for participation will be identified by communication with the general surgery house staff and attendings. Outpatients and inpatients at University Hospital in Newark, NJ will be screened. Outpatients will be approached for study participation either in the outpatient office or in UH on the morning of surgery. Inpatients will be approached for study participation, either the day before or on the morning of the surgery.

VII.2 Randomization: Eligible and consenting subjects will be enrolled and randomized. A randomization table was created using a table of random numbers to assign subjects to RIPC and No RIPC groups. Subjects will be randomized in blocks of 6 to ensure equal randomization into the two groups. The randomization table has been entered into the REDCAPs program. After enrollment, the research team member who will conduct the intervention will access the REDCAPS program online immediately before the induction of anesthesia and obtain group assignment. **VII.3 Masking:** The study will be conducted in a double-masked fashion. Investigative team member/s that will carry out randomization and administer the intervention will not be involved in evaluation of clinical and laboratory outcomes. The primary surgical team, nurses, and any consulting services caring for the patient will be unaware of the group assignment. Other care providers will not be informed of the group assignment. Outcome assessors will not be involved in randomization and administration of the RIC intervention. Adequate steps are in place to mask the outcome assessors (clinical and laboratory) from knowing group assignment.

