- 4. Peripheral blood leukocyte gene expression profiles determined by RNA sequencing.

Commercially available kits will be used for the plasma assays in section VIII.3.

IX. Data Collection and Analysis:

IX.1 Data Collection, and Study Variables

Data regarding subject screening for eligibility, recruitment, and enrollment will be stored in an Excel file on a dedicated Rutgers server with password protection. Other data will be entered electronically into case report forms via the online REDCaps software. Hard copy case report forms are also available as needed to facilitate the transfer of data to online software.

IX.2 Case Report Forms (CRFs)

5 CRFs will be used to collect study-related data as follows.

- CRF 1 will capture baseline characteristics. Variables collected will include age, sex, ethnicity, height, weight, baseline medical characteristics, length of hospital stay, baseline laboratory values, and care needs at the time of surgery (whether hospitalized, in ICU, etc).
- CRF 2 will capture operative information. Variables will include the type of surgery, date, time, and duration of surgery, blood loss and fluid replacement.
- CRF 3 will capture intervention-related data, including time of intervention, patient's systolic blood pressure and tourniquet pressure used, patient's pain scale as a result of the intervention, and whether or not the intervention was completed.
- CRF 4 will capture complication related data. All post-op complications will be graded I V according to the Clavien-Dindo grading scale.² The number of each type of complications will be recorded. This data will be used to calculate CCI using an online calculator available at www.assesssurgery.com.¹
- CRF 5 will capture data related to the molecular studies as discussed previously.

IX.3 Data Analyses

Methods of proposed data analyses are described in the Statistical analyses plan section, Appendix C.

X. Risks and Benefits

X.1 Risks to Subjects

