#### VI.4 Sample size and power

There is no data available in the literature regarding the potential benefits of RIC on global assessment of postoperative complications. Clinical trials of remote ischemic preconditioning, thus far were aimed at decreasing organ-specific complications such as myocardial infarction, acute kidney injury, stroke, etc. Data from animal studies of remote ischemic preconditioning or per- and postconditioning does not provide appropriate information. Therefore, evidencebased and realistic projections of effect size of the proposed intervention are not feasible. Hence, sample calculations and estimates of power were not pursued. It is anticipated that data on complications from this pilot study would assist in more informed calculations of sample size and power for future studies of similar nature.

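### The primary CCI test is valid but ignores operation type and age, and no planned analysis gives a treatment effect adjusted for them

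*SAP*

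**What the plan says.** - **Primary analysis.** SAP V.1: "One of two independent sample tests, a t test or Mann-Whitney test depending on the normality of distribution, will be used". A transformation may be applied first. The significance rule is "P values of 0.05 will be considered significant". No covariate enters this comparison.
- **Prognosis.** After giving an overall complication rate in general surgery, the Protocol Background adds: "This proportion increases with the complexity of the surgery". It does not say by how much.
- **Case mix.** Appendix A lists 16 categories, from hiatal hernia repair and stoma takedown to pancreatic resection, esophagectomy, HIPEC and open aortic aneurysm repair. Other operations may be added if the study and surgical teams agree.
- **Randomisation.** Protocol VII.2: "Subjects will be randomized in blocks of 6 to ensure equal randomization into the two groups". No stratification factor is described. The assignment is obtained just before anesthesia is induced.
- **Data available.** CRF 1 records age. For CRF 2, Protocol IX.2 says: "Variables will include the type of surgery, date, time, and duration of surgery, blood loss and fluid replacement".
- **Other models of CCI.** SAP V.1 and SAP VI.4 (Exploratory analyses) plan regressions that test whether age, sex and duration of surgery each interact with RIC. Operation type appears in none of them.
- **Size.** SAP VI.4 (Sample size and power): "Hence, sample calculations and estimates of power were not pursued". No number of subjects is given.

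**The concern.** The plan names a factor that drives complications, lets it vary widely and records it, but controls it neither in the randomisation nor in the analysis. Blocks of 6 keep the arms equal in number; they do not balance the type of operation. Variation in CCI due to the operation therefore stays in the error term, and if one arm happens to receive more of the complex operations, the observed difference moves with it.

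This matters because of what the trial is for. Protocol section II wants better estimates of CCI with and without RIC, to decide whether larger trials should follow. The SAP repeats the purpose: "It is anticipated that data on complications from this pilot study would assist in more informed calculations of sample size and power". A difference shifted by case mix would pass into that decision. Baseline tables may reveal an imbalance but cannot correct the result, and an adjustment chosen after seeing them would be post hoc.

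**Working it through.** The plan states no sample size, effect size or SD, so there is no figure to reproduce. Every input below is an assumption unless a source is named.

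**1. How often would case mix be unbalanced?** Assume 30 per arm and half of the operations complex.
- If each subject is complex independently with probability 0.5, the complex share differs between arms by at least 10 points (3 subjects) in 52% of trials, and by at least 20 points (6 subjects) in about 16%. With 30% complex, the 10-point figure is 48%.
- If exactly 30 of the 60 are complex, the figures are 44% and 20%. They differ because the gap in counts is then always even, so a gap of 3 cannot occur.
- With half complex (total fixed), a gap of at least 20 points falls to 4.7% at 102 subjects in all and 0.4% at 198.

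**2. How far would that move the CCI difference?** Assume mean CCI of 6.7 for less complex and 21.5 for complex operations, and no RIC effect.
- Shift = imbalance × (21.5 − 6.7) = imbalance × 14.8.
- 10 points: 0.10 × 14.8 = 1.5. 20 points: 0.20 × 14.8 = 3.0.

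**3. Compared with the standard error.** In a simulation with these means, operation class and age together gave R² = 0.113 on the raw scale and 0.125 on ranks.
- Variance due to class = 0.5 × 0.5 × 14.8² = 54.8.
- Total variance is at least 54.8 / 0.113 = 485, so SD is about 22.0.
- SE of the difference = 22.0 × √(2/30) = 5.7.
- A 10-point imbalance is then 1.5 / 5.7 = 0.26 SE, and a 20-point imbalance is 3.0 / 5.7 = 0.52 SE.

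**4. What does adjustment gain?**
- The simulated ratio of unadjusted to adjusted variance was 1.08 to 1.12, worth 8-12% more subjects. The SE falls from 5.7 to between 5.7/√1.12 = 5.4 and 5.7/√1.08 = 5.5.
- Under an assumed benefit, rejection rose from 23.4% to 24.8% at 30 per arm, and from 33.7% to 36.3% at 50 per arm.
- For other prognostic strengths, the adjusted SE is about √(1 − R²) times the unadjusted one. The table takes a standardised effect of 0.5 and two-sided alpha of 0.05.

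| R² | SE multiplier | Power, 60 in all | n per arm for 80% power |
|---|---|---|---|
| 0 (unadjusted) | 1 | 0.49 | 63 |
| 0.05 | 0.975 | 0.51 | 60 |
| 0.10 | 0.949 | 0.53 | 57 |
| 0.20 | 0.894 | 0.58 | 51 |
| 0.30 | 0.837 | 0.64 | 44 |

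**5. Is the planned test valid?** A second simulation used no RIC effect, blocks of 6, 60 subjects and a CCI-like score with many zeros. Complication rates were 25% and 55% by complexity (R² about 0.07), or 15% and 70% (R² about 0.19).
- Over all trials, type I error was 0.047-0.048 (t test), 0.048 (Mann-Whitney) and 0.046-0.049 (adjusted linear model). The mean difference was near zero.
- In trials with at least 20 points of imbalance, the unadjusted difference shifted by 2.2 to 3.7 CCI points. False positives were 6-9% (t test) and 8-11% (Mann-Whitney). Adjusted, the shift was about 0.3 or less and false positives were about 4%.

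**The case against.** The strongest reply is that a randomised comparison needs no covariates. Chance imbalance in case mix is already part of the standard error and p value, so this is a preference about precision and not a defect. That stands as far as validity goes. A reader might infer from the mixed operations and the lack of stratification that the primary test is biased or has an inflated error rate. Neither follows: step 5 shows an overall error near 5% and no average bias, and the higher false-positive rates apply only to the minority of trials with a marked imbalance.

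It is also fair that the gain is small on these inputs, since a typical shift is a fraction of one SE and the estimate stays imprecise after adjustment. A reader might also take it as given that the trial is small. The documents give no number; the only support is the pilot and Phase IIa labels, and at about 200 subjects large imbalance is rare.

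Two replies carry less weight. The exploratory regressions would ordinarily include main effects of age, sex and duration, but they are there to test interactions and do not specify an adjusted RIC effect. Actual duration, moreover, is known only after assignment, so it is a poor stand-in for the planned operation. As for cost, CRF 2 is described as recording operative information, not the planned procedure. Eligibility, however, is judged on the expected operation, so the planned procedure must already be known at screening.

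**Conclusion.** The point holds as a question of efficiency and robustness. The primary test is valid but sets aside two prognostic variables that the trial collects, one of which the protocol itself ties to complications, and no planned analysis supplies an adjusted effect.

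With 30 per arm and R² of about 0.11-0.13, adjustment is worth about 8-12% in effective sample size. It also protects the estimate in the trials where case mix happens to be uneven. At R² of 0.30 the sample size for 80% power would fall from 63 to 44 per arm; at 0.05 it would fall only to 60. Trial size, share of complex operations, CCI means and R² are all assumed. What does not rest on them is that the adjustment was available and is not pre-specified. It is a recommended change because it costs little, not because the plan is unsound.

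**What to change.** In SAP V.1, pre-specify as the main result a covariate-adjusted difference in CCI with a 95% confidence interval, for example from a linear model with robust or permutation-based inference, given the many zeros expected. Rank ANCOVA, a van Elteren test or a proportional-odds model would not by themselves give a difference in CCI points, which is what the next trial needs.

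- Adjust for age and planned operation class. Group the Appendix A list into a few levels, with one for added operations, and fix the grouping before unblinding.
- Take the class from the operation on which eligibility was judged, not the one performed.
- Do not adjust for actual duration of surgery.
- Report operation class by arm, and keep the unadjusted t or Mann-Whitney test as supporting.

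The cost is SAP wording, a short grouping table and a few lines of code, with no extra subjects or visits. There is a small downside: the grouping has to be agreed in advance and kept coarse to avoid sparse levels, and the planned operation must be carried from screening into the analysis data.

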### V.2 Secondary endpoints

For endpoints that are continuous variables and are not normally distributed log transformation will be explored to achieve normality. Length of hospital stay will be compared with either a t test or Mann-Whitney test. Counts and proportions experiencing 30- day mortality will be reported. No formal intergroup comparison will be conducted regarding hospital stay and 30-day mortality.

The analyses to address the effects of RIC on plasma cytokines, acute phase response, complement activation and leukocyte gene expression will be considered independent of each other. Although these groups of outcomes are interconnected as a global innate immune responses to surgery or other injury it is quite likely that RIC may only modulate one or more rather than all the measured outcome subgroups. Furthermore, it is quite likely that RIC may modulate only one or few of the analytes in a particular subgroup

Repeated measures of continuous variables of inflammation, acute phase response and complement activation in two independent groups will be analyzed with mixed analyses of variance (ANOVA) to examined for interaction between treatment and time. If the omnibus p value is significant then additional post hoc tests will be conducted in appropriate groups. Because of the pilot nature of the study no adjustments will be made to the p values in the post hoc tests. P values <0.05 will be considered significant.

Leukocyte gene expression will be examined using RNA sequencing. Five to ten replicates in each group will be examined at baseline and postoperative day 2. A sequencing depth of 10 million reads will be utilized. Differential gene expression analyses will be performed. For individual genes with a relatively higher levels of expression relative fold changes of  $\geq$  2.0, and or p values of < 0.01 will be considered significant.

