Remote Ischemic Conditioning (RIC) to Decrease Postoperative Complications After Major Abdominal Surgery - A Phase IIa Trial

NCT03234543

09/08/2017

I. STUDY TITLE: Remote Ischemic Conditioning (RIC) to Decrease Postoperative Complications After Major Abdominal Surgery - A Phase IIa Trial

II: STUDY GOALS AND OBJECTIVES:

1. To obtain preliminary data regarding postoperative complications in subjects undergoing abdominal surgery and receiving remote limb ischemic or sham conditioning.

Subjects undergoing abdominal surgery will be prospectively randomized in equal proportions to receive either remote or sham lower limb ischemic conditioning immediately before surgery commences and on postoperative days 1 and 2. Each intervention will comprise 3 cycles of 5/5 minutes of inflation/deflation of a pneumatic cuff on mid-thigh. Postoperative complications within 30 days after surgery will be evaluated using Comprehensive Complication Index (CCI)¹, a continuous, scaled (0-100) and a validated measure of the total complications burden.

The preliminary data is expected to help in determining whether larger trials of RIC to decrease postoperative complications should be pursued, and provide more reliable estimates of CCI without and with RIC, sample sizes and power in design of larger trials.

2. To test whether remote limb ischemic conditioning (RIC) decreases systemic inflammatory response in patients undergoing major abdominal surgery.

Time-dependent differences between the two groups in plasma levels of inflammatory cytokines (TNF-a, IL - 1β , 6, 8 and 10), acute phase proteins (C reactive protein [CRP], alpha-1-acid glycoprotein, fibrinogen [FGN], and haptoglobin) complement components (C2, C4b, C5, C5a, and C5b-9), and blood leukocyte gene expression at baseline and one hour after completion of surgery and the second and third interventions will be tested for significance. It is hypothesized that RIC would decrease systemic inflammatory response to major surgery.

III: BACKGROUND:

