Subjects will be masked from recognizing which group they are in in the following manner: a) Subjects will not be informed of the group assignment throughout their participation in the study; b) subjects randomized to No RIPC will have a tourniquet placed on the thigh and inflated. It is anticipated that the subject is likely to perceive the inflation as the true RIPC. No information will be provided to subjects regarding the amount of pressure used to inflate the tourniquet in either group.

VII.4 RIC Intervention and Perioperative Care: Sham and RIC interventions will be as described above in section V. All other aspects of anesthesia care will be as per standards of practice. All aspects of the surgical procedure and postoperative care including decisions regarding discharge will be as per standards of practice. The diagnosis and treatment of complications will be under the purview of the clinical care team. The research team will not participate in the clinical care of the subjects.

VII.5 Blood Sample Collection and Processing: Ten mL of venous blood (10mL) will be collected at baseline, an hour after completion of skin closure, and an hour after completion of second and third RIC interventions. 2.5 mL will be placed in PAXgene Blood RNA tubes (Qiagen) for RNA isolation from leukocytes. RNA will be submitted to our Molecular Resource Facility for RNA sequencing. Remaining blood will be placed in EDTA tubes, centrifuged at 3500 rpm and plasma will be stored in aliquots at -70^oC.

VIII. Outcomes:

VIII.1 Primary Outcome:

The CCI, a validated and scaled score of all surgical complications (range 0 [no complications] to 100 [death]) is the primary outcome.

All complications within 30 days after surgery will be graded as per Clavien-Dindo classification.^{1,2} CCI will be computed for each subject using the publically available website, http://www.assessurgery.com/. Follow up after discharge will occur either in clinic or via telephone

VIII.2 Secondary Clinical Outcomes:

- 1. Proportion of patients in each group that complete all three RIC interventions
- 2. Hospital days

3. 30-day mortality (will be captured as part of CCI)

VIII.3 Secondary Molecular Outcomes:

- 1. Plasma cytokines levels (TNF-a, IL 1β , 6, 8 and 10)
- 2. Plasma acute phase reactant proteins (CRP, alpha-1- acid glycoprotein, FGN, and haptoglobin)
- 3. Plasma complement levels (C2, C4b, C5, C5a, and C5b-9)

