# VI. Other considerations

#### VI.1 Missing data

**Endpoints:** The number of subjects in whom data would be missing is expected to be low due to the prospective nature of the study. The pattern of missing data will be described. Subjects with data missing for a particular outcome would be excluded from that analysis. Additional decisions about handling missing data would be made prior to any intergroup comparisons are performed.

**Baseline values of continuous endpoints**: Subjects in whom a baseline value of a continuous variable such as the laboratory analytes is missing will be included in the analyses of that outcome. A missing indicator approach, a valid method for prerandomization measures will be used.

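### SAP V.2 tests the plasma markers only by treatment-by-time interaction and leaves baseline's role unstated, so VI.1's missing-indicator rule does not fit the likeliest model and power for a sustained lowering is generally reduced

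*SAP*

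**What the plan says.** SAP V.2 covers cytokines, acute phase proteins and complement together. The repeated measures "will be analyzed with mixed analyses of variance (ANOVA) to examined for interaction between treatment and time". It continues: "If the omnibus p value is significant then additional post hoc tests will be conducted in appropriate groups". The threshold is 0.05. V.2 names neither a treatment main effect nor an average effect, and does not say whether baseline is a response or a covariate.

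Three other places bear on baseline:

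- Protocol section II, Objective 2, speaks of "Time-dependent differences between the two groups in plasma levels of inflammatory cytokines" and of the other marker classes, "at baseline and one hour after completion of surgery and the second and third interventions will be tested for significance". Its hypothesis has a direction: "It is hypothesized that RIC would decrease systemic inflammatory response to major surgery".
- Protocol VII.5 sets four blood samples, which "will be collected at baseline, an hour after completion of skin closure, and an hour after completion of second and third RIC interventions".
- SAP VI.1 says that subjects whose baseline value of a continuous variable such as "the laboratory analytes is missing will be included in the analyses of that outcome", and gives the method: "A missing indicator approach, a valid method for prerandomization measures will be used". The same section excludes subjects from any analysis whose outcome they lack.

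SAP VI.4 (Exploratory analyses) reuses the mixed ANOVA for interactions of age, sex and duration of surgery with RIC.

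**The concern.** Two analysts following this SAP in good faith could fit different models, and neither model serves the whole plan. With baseline as a time level it is a response, so there is no covariate to fill in and flag. A classical mixed ANOVA then needs all four values and drops the subjects that VI.1 says are kept. With baseline as a covariate VI.1 works, but the named interaction then compares only three postoperative times and cannot see a shift of equal size at all of them.

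The hypothesis is that RIC lowers the response. A lowering that lasts across the postoperative samples is one natural form of that, and the named test is not the efficient one for it. Because the post hoc comparisons open only after a significant omnibus result, a missed interaction closes them for that marker.

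**Working it through.** **Text.** Objective 2 lists baseline among the tested times, and VII.5 gives four samples. Four time levels is therefore the better supported reading. A covariate role is implied only by the method in VI.1. On the four-level reading, a subject without a baseline value falls under two opposite rules in VI.1: keep (baseline rule) and exclude (outcome rule). A likelihood-based mixed model could keep the subject, but not through a missing indicator.

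**Inputs for power.** From the documents: four times, equal allocation, alpha 0.05. The documents give no sample size, SD, effect or correlation and no power figure to reproduce. Assumed: n = 30 per arm, postoperative SD 1, one common correlation ρ of 0.3/0.5/0.7, and a difference d = 0.6 SD at all three postoperative times and 0 at baseline. Power comes from the non-central F distribution.

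**Four-level interaction.** F(3, 3(2n−2)), λ = n·Σ(dᵢ − d̄)²/(2(1−ρ)). The sum is 0.75 × 0.36 = 0.27. At ρ = 0.5, λ = 30 × 0.27/(2 × 0.5) = 8.10.

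**Baseline-adjusted joint test of the three postoperative differences.** F(3, 2n−5), λ = (n/2)·3d²/[(1−ρ)(1+3ρ)] ÷ (1 + 1/(2n−4)). At ρ = 0.5, λ = 15 × 1.08/(0.5 × 2.5) ÷ (1 + 1/56) = 12.96/1.0179 = 12.73.

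**Three-level interaction (baseline as covariate).** All three differences are equal, so λ = 0 and power equals alpha.

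| Equal SDs, constant 0.6 SD | ρ 0.3 | ρ 0.5 | ρ 0.7 |
|---|---|---|---|
| λ, four-level interaction | 5.79 | 8.10 | 13.50 |
| λ, joint adjusted | 11.97 | 12.73 | 17.11 |
| Power, four-level interaction | 49% | 65% | 88% |
| Power, joint adjusted | 81% | 83% | 93% |
| Power, three-level interaction | 5% | 5% | 5% |
| Arm size for 80% power, four-level / joint | 58 / 30 | 42 / 28 | 25 / 22 |

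**Growing effect (0.2, 0.4, 0.6 SD).** Four-level 37/51/75%, joint 56/62/79%, three-level 19/26/41%.

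**Effect at one sample only (0.6 SD).** Four-level 49/65/88%, joint 51/65/86%. With 20 per arm: 34/46/70% versus 34/44/66%.

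**Baseline SD half the postoperative SD, constant 0.6 SD.** Classical ANOVA (simulated) about 61/76/90%, joint 81/84/93%. An interaction test with unstructured covariance works on changes from baseline. Those changes have variance v = 0.25 + 1 − ρ and covariance c = 0.25, and λ = (n/2)·3d²/(v + 2c) = 16.2/1.45, 16.2/1.25 and 16.2/1.05 = 11.17/12.96/15.43, giving about 78/84/90%. The joint test differs from it by about −1 to +3 points.

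**Same half SD, effect at one sample.** In simulation the classical ANOVA has about 55/70/89% and the joint test about 51/65/86%. Separate runs put the largest loss at about 5 to 6 points.

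**Missing baselines alone (ρ = 0.5, constant 0.6 SD, 5/10/20% missing).** Replacing n by n(1−m) in the four-level formula, power falls from 65% to 62/60/54%, a loss of 2.5/5.2/10.9 points. The joint test with indicator falls from 83% to 82/81/78% (simulated), and on complete cases to 81/79/72%. At ρ = 0.7 the indicator is no better than complete cases (91/90/84% versus 92/91/85%).

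**The case against.** The strongest reply is that the interaction is a legitimate choice. Objective 2 asks for time-dependent differences, a four-level interaction answers that, and no document says the effect is constant across the postoperative samples. This stands: the test is valid, and its disadvantage depends on the pattern. The gap is about 6 points at ρ = 0.7 (88% versus 93% after rounding), and nil or reversed for an effect at one sample.

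The background in the protocol describes surgery raising these markers, so baseline may vary less than later values. That also stands. With half the baseline SD the gain over classical ANOVA is about 20/8/3 points, and over an unstructured-covariance interaction test there is little or none. Part of the gain is thus covariance handling.

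These are secondary markers in a self-described pilot with no planned power. VI.1 expects few missing data and leaves further missing-data decisions open until before intergroup comparison. The direct cost of missing baselines is indeed small. Pilot status may excuse unadjusted p values and absent power, but it does not settle which model is to be fitted.

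Two stronger readings are tempting and unsupported. A reader might infer that the planned test cannot detect a sustained lowering at all. That is true only on the three-level reading, which Objective 2 and VII.5 make the less likely one. A reader might also infer that a non-significant omnibus result ends all analysis of a marker. Only the post hoc comparisons are closed: the exploratory models in VI.4 and the analyte p values in VI.2 are still reported.

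**Conclusion.** The mismatch between V.2 and VI.1 is real and rests on the text alone. No reading both lets VI.1 operate and gives the named test power against a constant lowering. On the better supported four-level reading the named test is valid but generally less powerful for a sustained lowering: 49/65/88% versus 81/83/93% in the main illustration.

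Those figures rest on an assumed arm size, effect, equal SDs and common correlation, so they show direction and rough size and do not predict this trial's power. The advantage is modest at high correlation, smaller when baseline varies less, and can turn into a loss of up to about 6 points for an effect at one time. Missing baselines alone cost about 2.5 points at 5% missing, so they are not the main reason to change. CCI is unaffected. This is a cheap improvement to the secondary marker analysis.

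**What to change.** In V.2, model the three postoperative samples (log scale where needed) in a repeated-measures mixed model with treatment, time, treatment-by-time and baseline as covariate, with unstructured covariance where feasible. VI.1's missing indicator then applies as written. Name the joint treatment effect over the three postoperative times as the omnibus test that opens the post hoc comparisons, and still report the interaction. Give baseline the same role in the exploratory models of VI.4.

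A joint test is preferable here to a single average-effect test. For 0.8 SD at one time (30 per arm, ρ = 0.5) an averaged adjusted test has about 35% power, against 90% for the four-level interaction.

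A constrained longitudinal model that keeps baseline as a response, with VI.1 reworded to match, is an acceptable alternative.

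The cost is SAP wording and a standard procedure, settled before any intergroup comparison, with no extra patients or assays. The price is little gain, or the small loss noted above, if the effect is confined to one sample.
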